3.11.3. Safety outcomes

- *Clostridioides difficile*-associated diarrhea⁴¹
 - Diagnosed according to the 2017 Infectious Diseases Society of American Clinical Practice Guidelines for *Clostridium difficile* Infection in Adults:
 - Unexplained and new-onset ≥3 unformed stools in 24 hours with a positive *Clostridioides difficile* toxin gene polymerase chain reaction assay
- Type one (immediate-type) hypersensitivity reactions⁴²
 - Acute symptom onset (minutes to hours) involving the skin, mucosal tissue, or both (e.g., generalized hives, pruritus or flushing, swollen lips-tongue-uvula) and at least one of the following (a through c):
 - a. Respiratory compromise
 - b. Reduced blood pressure
 - c. Signs of end-organ dysfunction
- Gallbladder disease³⁷
 - Diagnosed sonographically as an echo without acoustical shadowing suggesting sludge and the presence of ceftriaxone-calcium salt

3.12. Post-resuscitation Care

All OHCA patients are admitted to or co-managed by the Neurocritical Care or Critical Care team at xxxx. The Neurocritical Care team has 24/7 coverage 365 days a year by an attending physician and an advanced practice provider (i.e., Physician Assistant or Nurse Practitioner). Most patients are treated in the cardiac ICU, but some may be treated in another ICU per bed availability and nursing.

xxxx has managed over 1,000 patients with TTM after OHCA and it is the largest hospital in xxxx. Patients will receive early coronary catheterization, when appropriate, and will undergo multimodal delayed neurologic prognostication according to clinical practice guidelines. All care will be the same in each study group except for the study drug.

3.12.1. Targeted temperature management

Patients unable to follow simple verbal commands after ROSC will be treated with TTM.⁵ If hypothermia is indicated, patients will be sedated and may receive a dose of a paralytic or chilled saline (4°C), and cooled to a target temperature. If normothermia is the targeted temperature (37.8°C) the same

interventions may be necessary, but will not be required. The Bard Medical Arctic Sun Temperature Management System[®], a servo-controlled surface cooling device, will be used as needed to achieve the target temperature at xxxx.

If patients are cooled, after 24 hours, they are re-warmed over 12-16 hours, and then maintained at 36.5°C-37°C until 72 hours after ROSC. Modifications to the protocol are allowed, such as targeting 36°C in the setting of refractory shock or uncontrolled bleeding, and delayed re-warming if refractory seizures are present. The trial protocol may be amended to incorporate data from the TTM-2 trial comparing 33°C for 24 hours with normothermia (37.8°C).⁴³

3.12.2. Sedation and analgesia

Propofol is preferred and is titrated by bedside nurses. Analgesia is provided with intermittent injections of fentanyl or a continuous infusion. As needed doses of midazolam may be administered. Low doses are maintained to avoid accumulation in the setting of end-organ dysfunction and temperature-mediated decreases in drug metabolism and elimination. The approach to sedation between centers may differ.

During rewarming, all sedation is interrupted. Dexmedetomidine infusion is often initiated to provide a cooperative level of sedation without respiratory depression. The Sedation-Agitation Scale is used and patients are often maintained at a score of 3-4 (Appendix 16.3). Analgesia is monitored with the Numeric Rating Scale in communicative patients and with the Critical Care Pain Observation Tool (Appendix 16.4) in those who are not communicative.

3.12.3. Shivering

Shivering is suppressed with focal counter-warming using a Bair Hugger System^M. The Bedside Shivering Assessment Scale (Appendix 16.5) and BIS electromyographic activity are monitored. Vecuronium may be administered when the BSAS is \geq 1. Magnesium is generally maintained \geq 2.4 mg/dL. In refractory cases, dexmedetomidine or magnesium sulfate infusion may be administered. Increasing the target temperature may also be tried.

3.12.4. Seizures and epileptiform activity

Patients may be monitored with cEEG until they have awoken or it is deemed not clinically necessary. Tracings are read by epileptologists throughout the day and concerning findings are reported to the bedside treatment team. Seizures and epileptiform activity will be classified according to the International League Against Epilepsy, Neurocritical Care Society, and American Clinical Neurophysiology Society's criteria. Antiepiletpic medications may be administered. Seizure prophylaxis with an antiepileptic medication is not standard care.

3.12.5. Hemodynamics

Clinical practice guidelines suggest keeping the MAP >65 mmHg, at a minimum, with observational data supporting a MAP 80-90 mmHg.⁵ MAP will be maintained >80 mmHg, unless it compromises the hemodynamics. Vasoactive medications, inotropes or mechanical circulatory support may be needed.

3.12.6. Best practices

Patients will receive stress ulcer prophylaxis. Venous thromboembolism prophylaxis will be administered unless contraindicated or there is a need for systemic doses. A bowel regimen will also be administered. Blood glucose may be maintained between 120-180 mg/dL.

3.12.7. COVID-19 considerations

Patients will be tested for, treated and monitored for COVID-19 per local hospital protocol at XXXX. Because the COVID-19 pandemic is evolving, adjustments may be necessary during the trial.

3.13. Neurological Prognostication

Patients who remain comatose will have their neurological prognosis assessed per the ERC's and the European Society for Intensive Care Medicine recommendations (Appendix 16.6).⁴⁴ The multimodal neurological prognostication algorithm will be activated >72 hours after ROSC to avoid confounding from acute metabolic disturbances, sedation, analgesia and paralysis.

3.13.1. Physical examination

Absent or extensor motor response to pain at >72 hours after ROSC in a patient who is not impacted by sedation may be indicative or a poor prognosis. Bilateral absence of pupillary and corneal reflexes at >72 hours or more after ROSC may be indicative of a poor prognosis.

3.13.2. Continuous electroencephalography

Patients may be monitored with cEEG until they have awoken or it is deemed not clinically necessary. A cEEG pattern considered malignant or without reactivity to sound or pain >72 hours after ROSC may be indicative of a poor prognosis.

3.13.3. Bispectral index

Patients may be monitored with the BIS until they have awoken or it is deemed not clinically necessary. Values <22 following the first dose of a paralytic and suppression ratio at six hours post-ROSC have been associated with poor prognosis and may be used.

3.13.4. Brain computed tomography

Brain computed tomography may be conducted for unwitnessed OHCA or if clinically warranted based on the opinion of the bedside treatment team. Evidence of diffuse hypoxemic-ischemic injury with reduced grey/white matter differentiation and sulcal effacement may be indicative of a poor prognosis.

3.13.5. Brain magnetic resonance imagining

Brain magnetic resonance imaging may be obtained >72 hours after ROSC in patients who remain comatose. Evidence of diffuse or bilateral multifocal hypoxic-ischemic lesions may be indicative of a poor prognosis.

3.13.6. Neuron specific enolase

Neuron specific enolase may be assayed at 24, 48 and 72 hours after ROSC. Values >90 mcg/L may be associated with poor outcome, while values <17 mcg/L may be associated with a favorable outcome. Consistently up-trending values may also indicate a poor outcome.

3.13.7. Somatosensory evoked potentials

Somatosensory evoked potentials may be evaluated >72 hours after ROSC in patients who remain comatose. Absent N20-responses bilaterally may be indicative of a poor prognosis.

3.14. Withdrawal of life supporting therapies

All patients will be treated for at least 72 hours unless any of the following occur: 1) it is deemed unethical to continue due to irreversible organ damage or documented medical comorbidity, 2) brain death has been established. In the event of brain death, patients will be classified as dying, and not support withdrawn. Diagnosis of brain death will follow the American Academy of Neurology guidance.⁴⁵

3.15. Follow-up

Patients will be followed for the duration of their hospitalization and up to six months after cardiac arrest. At the time of hospital discharge, a research coordinator will determine each patient's mRS score and CPC. This will also occur at six months after cardiac arrest via telephone call.

3.16. Co-enrollment

Co-enrollment in other clinical trials, observational studies and registries was reviewed. Patients enrolled in the PROTECT trial may be co-enrolled in other interventional trials if deemed appropriate by the clinical trial steering committee.

3.16.1. ICECAP

The Influence of Cooling Duration on Efficacy in Cardiac Arrest Patients (ICECAP) trial is an adaptive study to determine if increasing durations of TTM are associated with good neurological outcome.⁴⁶ Patients may be co-enrolled in ICECAP and PROTECT.

3.16.2. PRECICECAP

PREcision Care In Cardiac ArrEst-ICECAP (PRECICECAP) uses novel, data-driven approaches to collect high resolution monitoring data from patients and will use that multi-parametric data to develop newly defined patient sub-groups with differing clinical trajectories and responses to therapies.⁴⁷ Patients may be co-enrolled in PROTECT and PRECICECAP.

3.16.3. INTCAR

The International Cardiac Arrest Registry is a worldwide repository of post-resuscitation cardiac arrest care.⁴⁸ Contributing centers input data into the INTCAR registry including cEEG, neurological imaging and neurological prognostication, amongst others. Because the registry is non-interventional, patients may be enrolled in PROTECT and contribute data to INTCAR.

3.16.4. PCAS

The PCAS study is examining cardiac arrest-associated neutrophils (CAAN) effect of CD73+ lymphocytes on neutrophil activation. Subjects enrolled the PROTECT trial will not be separately enrolled in PCAS as the analyses are the same.

4. Resistome Assessment

4.1. Specimen Handling and Transportation

Sputum sample and rectal swab will be collected prior to study drug initiation and 72-96 hours after administration of first dose of study drug (after study drug has been completed). A third rectal swab will be collected 144-168 hours after administering first dose of study drug or earlier in the case of death, comfort measures only or hospital discharge, after which no study procedures will be conducted. Missing time points do not disqualify patient for study participation and is not a protocol deviation. Total nucleic acids will be extracted and resistomes determined by shotgun metagenomic sequencing using super high-throughput methods. COVID-19 considerations are outlined in Appendix 16.7. Samples from non-XXXX hospitals may be stored and transported under various conditions not listed above but that are acceptable.

4.2. Resistome Determination

Antibiotic resistance genes were measured in material recovered from rectal swabs collected prior to study drug initiation, after study drug completion (three days), and 6-7 days after the first dose of study drug. Total nucleic acids were extracted from rectal swabs using ZymoBIOMICS DNA/RNA plus extraction kit (Zymo Research Corporation 2024). Sequencing libraries were prepared using the Kapa BioSystems HyperPlus Kit (KR1145 -v3.16). Sequencing was completed on a NovaSeq 6000 with an SP flow cell (paired-end 250 bps reads). Data was demultiplexed using bcl2fastq v2.20.0.422. FASTQ files were examined for quality using FastQC v0.11.5 and multiqc v1.11 with default settings.^{49,50} Estimation of duplication rates, adapter sequence trimming and read merging was completed using fastp v0.23.2 with default settings and the flags '--include_unmerged', '--merge', '-I 50' and '-g' to remove poly-G tails produced by the NovaSeq platform.⁵¹ Human reads were identified by mapping the data against the human reference genome (GRCh38) using bwa mem v0.7.17 and filtering the mapped reads using samtools v1.19.2 (bit flags -f 4 -F262, -f 8 -F 260, and -f 12 and -F 256).^{52,53} Metagenomic assembly was completed from the unmapped reads using the SPAdes pipeline v3.15.5 with the metagenomic flag and default settings. QUAST v5.2.0 was utilized to characterize the contiguity of the genome assemblies.^{54,55} Per sequence coverage statistics were calculated using bwa mem v0.7.17 and samtools v1.19.2 with default settings. BLAST v2.14.0 was utilized to compare sequences against the nt database.⁵⁶ Blobtools v1.1.1 was then used to taxonomically classify each sequence using the 'bestsum' taxonomic rule and the NCBI taxonomy database.⁵⁷ Any human contigs were removed from the assemblies based on these taxonomic assignments. PROKKA v1.14.0 was used for CDS annotation. Antimicrobial resistance genes were characterized using AMRFinderPlus using both the genome assemblies (FASTA) and the annotated genes from PROKKA (FAA).^{58,59}

5. Inflammation Assessment

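### The first read filter printed in section 4.2 requires and excludes the same bit, so it selects no reads; the executed command should be checked and the value corrected

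*Combined protocol and SAP*

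**What the plan says.** Section 4.2 gives the sequencing pipeline step by step, in the past tense. The input is "paired-end 250 bps reads". Before any mapping, "adapter sequence trimming and read merging was completed using fastp v0.23.2", with options that write merged pairs and keep unmerged reads.

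Human sequence is then handled as follows: "Human reads were identified by mapping the data against the human reference genome (GRCh38) using bwa mem v0.7.17 and filtering the mapped reads". Three samtools settings are listed. The first two appear in "filtering the mapped reads using samtools v1.19.2 (bit flags -f 4 -F262, -f 8 -F 260"; the second and third together read "f 8 -F 260, and -f 12 and -F 256". After that, "Metagenomic assembly was completed from the unmapped reads using the SPAdes pipeline".

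Contigs classified as human are removed after assembly, and resistance genes are called on what remains. Section 9.5 compares antibiotic resistance gene (ARG) numbers within and between arms.

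The section does not give the command lines. It does not say how the three filter outputs were combined, whether merged reads were mapped as single reads, or how many reads each filter kept.

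**The concern.** The three settings look like a set meant to cover three situations: this read unmapped, its mate unmapped, and both unmapped. The second and third are coherent. The first asks for a bit and rejects it in the same command, so it can return nothing. The other two do not fill the gap, because both require the mate-unmapped bit.

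These reads are the raw material for the assemblies, and the assemblies are the raw material for every ARG comparison in section 9.5. The resistome is named in the trial title and in the hypothesis in section 2.7, and section 11 puts its results in the main publication. Section 4.2 gives software versions and flag values, so readers can be expected to follow it. Anyone who follows it literally would assemble from a read set that differs from the stated one.

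**Working it through.** The plan gives no figure to reproduce here; the check is bit arithmetic on the printed settings.

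**Inputs (section 4.2).** Filter 1: require 4, exclude 262. Filter 2: require 8, exclude 260. Filter 3: require 12, exclude 256.

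**Assumed meaning (standard samtools; not defined in the document).** `-f` keeps a read only if all listed bits are set, and `-F` drops it if any listed bit is set. Bits: 1 = paired, 2 = proper pair, 4 = read unmapped, 8 = mate unmapped, 64 and 128 = first and second read of a pair, 256 = secondary alignment. A flag value x passes if (x & f) = f and (x & F) = 0.

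**Step 1: does each filter contradict itself?**
- Filter 1: 262 = 256 + 4 + 2, so 4 & 262 = 4. Bit 4 is both required and excluded.
- Filter 2: 260 = 256 + 4, so 8 & 260 = 0. Coherent.
- Filter 3: 12 = 8 + 4, so 12 & 256 = 0. Coherent.

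**Step 2: how many of the 2^12 = 4,096 flag values pass?**
- Filter 1: 0.
- Filters 2 and 3: each fixes three bits, leaving 2^9 = 512.
- All three together: 0 + 512 + 512 = 1,024. Filters 2 and 3 do not overlap, because one excludes bit 4 and the other requires it.

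These are counts of possible bit patterns, not of reads.

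**Step 3: which kinds of read are affected?**

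| Read | Flag | Filter 1 as printed | Filter 2 | Filter 3 | Filter 1 with 264 |
|---|---|---|---|---|---|
| Both ends unmapped | 77 (64+8+4+1), 141 (128+8+4+1) | no | no | yes | no |
| Unmapped, mate mapped | 69 (64+4+1), 133 (128+4+1) | no | no | no | yes |
| Mapped, mate unmapped | 73 (64+8+1), 137 (128+8+1) | no | yes | no | no |
| Unmapped single read | 4 | no | no | no | yes |

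Pairs with both ends unmapped are kept by filter 3. Two kinds of unmapped read pass none of the printed filters: the unmapped mate of a half-mapped pair, and an unmapped single read. A merged pair mapped as a single read falls in the second group.

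**Step 4: sensitivity to a different value.** With 264 = 256 + 8, filter 1 passes 512 flag values and the total becomes 512 + 512 + 512 = 1,536. The added patterns are those with the read-unmapped bit set, and the mate-unmapped and secondary bits clear. They include both groups lost in step 3. With 258 = 256 + 2, filter 1 also passes 512 values and also picks up both groups, but it overlaps with filter 3 on flags 77 and 141.

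**The case against.** The strongest reply is that this is a one-digit slip in a methods sentence. It has real force. The partner that matches the other two filters is 264, one digit from 262, and that single change recovers every read type shown as lost above. The section reports that assembly and all later steps were completed. If all reads had been mapped as single reads and filtered as printed, there would have been no unmapped reads to assemble, which conflicts with the section's own account. That scenario therefore points to a misprint. A typing or text-conversion error cannot be excluded either; the printed setting lacks the space that its neighbours have.

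For reads kept as pairs, the possible loss is narrow. A fragment with neither end matching the human genome is still kept. The only lost read is one whose mate mapped to GRCh38. Both ends come from one DNA fragment, so that read may itself be human or ambiguous. The human-mapped mate that filter 2 retains is at least partly dealt with by the later removal of human contigs.

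A reader might infer that the pipeline discarded microbial reads and that the ARG counts are therefore wrong, or that lost reads would favour the hypothesis of no harm to the resistome. The documents support neither inference. They do not show that 262 was executed, and they give neither the size nor the direction of any effect. One filter is described for all samples, so nothing points to a difference between arms.

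What the reply does not remove is the contradiction in the printed value. The later removal of human contigs cannot restore reads dropped before assembly, and the text does not settle how merged reads were mapped.

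**Conclusion.** The printed filter 1 is wrong as written: under standard samtools rules it selects no reads, and the pipeline cannot be reproduced from section 4.2.

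The consequence is conditional. If 262 was only misprinted, the error is confined to the text. If it was run, the loss depends on how reads were mapped. With reads mapped as pairs, it is limited to unmapped mates in half-mapped pairs. It is wider if merged reads were mapped as single reads, because every unmapped one would be dropped. The merged fraction and the mapping mode are not stated, so no share of reads can be calculated. A misprint is at least as likely as a faulty run.

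The point bears on the ARG comparisons in section 9.5 only. It does not touch early-onset pneumonia, the listed secondary and safety outcomes, or the sample size in section 9.1. It rests on the standard meaning of the samtools options and flag bits, which the document does not define.

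**What to change.** 1. Check the script that was executed. The number of reads written by filter 1 is informative: a non-zero count means that the printed setting is not what ran.
2. Correct the value in section 4.2 to one that does not exclude bit 4, matching what was run. If 264 is that value, it also keeps unmapped merged (single) reads, so no separate extraction rule is needed.
3. In the same edit, it would help to state whether merged reads were mapped as single reads and how many reads each filter kept.
4. Only if 262 was actually run, redo read extraction, assembly and ARG calling for all samples, before the section 9.5 comparisons.

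The cost is a line or two of text if this is a misprint. Otherwise it is compute time, with no new samples.

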2.5. Antibiotic Resistance and the Resistome

The effect of antibiotic prophylaxis on bacterial resistance after OHCA are not known, but antibiotic resistance is a global concern.²⁵ Emergence of resistant bacteria will be examined in treatment and control patients. Control patients may be exposed to longer courses of broad spectrum antibiotics due to higher rates of pneumonia. Drug concentrations in stool, effects of ceftriaxone on expression of resistance genes, and on richness, diversity, and relative abundance of taxa will be quantified.

Prior studies have concluded antibiotic prophylaxis in acutely brain-injured patients does not induce bacterial resistance based on limited analyses. For example, in the trial examining cefuroxime prophylaxis, the intervention did not induce bacterial resistance based similar rates in gram-negative bacilli pneumonia in both groups.¹⁹ Advances in metagenomics allows for sample multiplexing and depth of sequence coverage (20 million reads) for the measurement of resistomes of each individual patient.

The ANTHARTIC trial evaluated intestinal acquisition of multidrug-resistant bacteria on day seven on solid selective media using stool samples, limiting their observations to conditionally cultivatable organisms.³ No difference was found following two days of amoxicillin-clavulanate administration compared to placebo. The contemporary gold standard for evaluating bacterial resistance is resistome analysis with high-throughput sequencing, which will be utilized in the PROTECT trial.

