2.7. Study Hypothesis and Anticipated Results

Prophylactic ceftriaxone administered within six hours of ICU admission will reduce the incidence of EOP and T cell-mediated inflammation in comatose OHCA survivors. Additionally, prophylactic ceftriaxone will not negatively affect bacterial resistomes as assessed by resistance genotypes in stool or sputum.

3. Trial Design

The PROTECT trial was a single-center, randomized-controlled, quadruple-blind, non-commercial superiority trial conducted at xxxx. The inflammation analysis will be completed at xxxx. The resistome analysis will be done at xxxx and xxxx.

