9.5. Resistome Assessment

Abundance of antibiotic resistance-associated genotypes in resistomes will be compared within and between treatment groups. If ceftriaxone or placebo alters resistomes, ANOVA will be performed across genotypes. The abundance of each genotype will be compared between ceftriaxone- and placebo-treated patients post-intervention by both Student's T test and $\chi 2$ to establish direct changes associated with ceftriaxone and whether those deviate from potential changes in resistomes due to ICU admission. All statistical analyses will be performed using GraphPad Prism 8 (GraphPad Software Inc). A p value <0.05 will be considered significant. To measure the acquisition of ARGs, the increase in number of ARGs relative to baseline samples were compared within each treatment group using the Wilcoxon Signed-Ranks test. In addition, the baseline number and changes in the number of ARGs targeting a prioridefined frequently administered (macrolides, beta-lactams, fluoroquinolones, sulfamethoxazole-trimethoprim, and vancomycin) and infrequently administered (tetracyclines, erythromycin, aminoglycosides, chloramphenicol, clindamycin, fosfomycin, quinupristin) antibiotics according to clinical practice guidelines were compared between treatment groups.^{67,68}

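### The resistance-gene count is not standardised for microbial sequencing depth, so it can change between visits or arms without any change in the resistome

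*Combined protocol and SAP*

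**What the plan says.** All references are to the combined protocol and SAP.

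- Section 4.2 maps reads to the human genome, filters out the matches and assembles the rest: "Metagenomic assembly was completed from the unmapped reads using the SPAdes pipeline v3.15.5 with the metagenomic flag and default settings". AMRFinderPlus is then run on the assemblies and on the genes annotated from them. Coverage is computed ("Per sequence coverage statistics were calculated using bwa mem v0.7.17 and samtools v1.19.2 with default settings"), but no use of it in counting or scaling ARGs is described.
- Section 9.5 defines acquisition through the count: "the increase in number of ARGs relative to baseline samples were compared within each treatment group using the Wilcoxon Signed-Ranks test". It also compares baseline numbers, and changes in number, between arms by antibiotic class, without naming a test. Separately, it compares genotype abundance within and between arms, but gives no unit or denominator.
- Section 2.5 gives the only depth figure: "depth of sequence coverage (20 million reads) for the measurement of resistomes of each individual patient". It does not say whether these are microbial reads, or reads as opposed to read pairs.
- Section 2.7 states the hypothesis: "prophylactic ceftriaxone will not negatively affect bacterial resistomes as assessed by resistance genotypes in stool or sputum".

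Sections 4.1, 4.2, 9.5 and 9.7 contain no subsampling, minimum microbial read count, spike-in, bacterial-load assay or depth covariate.

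**The concern.** An ARG enters the count only if the DNA that carries it is covered deeply enough to assemble. The count therefore reflects two things: which ARGs are present, and how many non-human reads the sample yielded. Randomisation balances the second at baseline but not afterwards, because antibiotics given after randomisation can change how much bacterial DNA a swab holds and hence what share of the reads is human. Section 4.1 adds further variation by accepting differing storage and transport conditions from other hospitals.

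If ceftriaxone lowers microbial reads, the count falls for reasons of measurement. That fall points the same way as the hypothesis in Section 2.7. A flat or non-significant within-arm signed-rank result could then be read as reassurance about resistance when it partly shows lost depth.

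**Working it through.** **Inputs.** The plan gives no sample size, effect size or power for the ARG count, so there is no figure of its own to reproduce. From the documents: 20 million reads (Section 2.5), 250 bp paired-end reads (Section 4.2) and 60 patients per arm (Section 9.1; an upper limit here, since Section 4.1 tolerates missed samples). The human-read share of rectal swabs, the community structure, genome sizes and the coverage needed to assemble are not given. They are assumptions below.

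**Model 1: detectable genomes at a given depth.** Coverage = non-human reads × read length ÷ genome size × the genome's share of microbial DNA. Assume 100 genomes, log-normal abundances (SD 2 on the log scale), 4 Mb genomes and 400 bp merged reads. At 10 million reads, 10,000,000 × 400 ÷ 4,000,000 = 1,000, so 5x coverage needs a share of 5 ÷ 1,000 = 0.5%. The true composition is held fixed.

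| Non-human reads | Share needed for 5x | Genomes at 5x | Genomes at 3x |
|---|---|---|---|
| 10 million | 0.5% | about 28 | about 37 |
| 3 million | 1.67% | about 12 | about 18 |
| 1 million | 5% | about 4 | about 7 |

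With the SD varied from 1 to 2.5 and either threshold, going from 10 to 3 million reads removes 48% to 73% of detectable genomes.

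**Model 2: detected ARGs at a given microbial share.** Fifty ARGs are truly present throughout. Coverage = 20,000,000 × 250 ÷ 5,000,000 × microbial share × genome share = 1,000 × microbial share × genome share, with 5x needed. Change in detected ARGs relative to a 70% microbial share:

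| Community | 50% | 30% | 10% |
|---|---|---|---|
| Middle case (50 genomes, SD 2) | −17% | −39% | −74% |
| Long tail (150 genomes, SD 2.5) | −20% | −45% | −79% |
| Few abundant genomes (20, SD 1), 20 million pairs | −2% | −8% | −39% |

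In the middle case the counts are 17.8 at 70%, then 14.8, 10.9 and 4.7.

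**Effect on a between-arm test.** Middle case, no true change, placebo at 70%, Mann-Whitney test on change in count, 1,000 simulated trials:

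| Ceftriaxone microbial share | Mean difference (ARGs) | False positives, n = 60 per arm | False positives, n = 30 per arm |
|---|---|---|---|
| 70% | 0 | 4% | 5% |
| 60% | −1.5 | 46% | 27% |
| 50% | −3.2 | 97% | 77% |
| 30% | −7.5 | 100% | 100% |

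**Masking.** In a long-tailed run with 5 ARGs truly added under ceftriaxone, a significant within-arm increase appeared in 65% of trials at equal microbial share and in 0% when the ceftriaxone share fell to 50%.

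**Enrichment of survivors.** Take Model 1 at 5x, with 20 of the 100 genomes resistant and the susceptible ones cut tenfold. Detected resistant genomes start at about 5.6 at 10 million reads. After the cut they are about 8.1 at 5 million, 6.3 at 3 million and a little under 5 at 2 million.

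**After standardisation.** Subsampling every sample in the between-arm simulation to 1 million microbial reads brings the mean difference to between −0.04 and 0 ARGs and false positives to 4–6%, whatever the ceftriaxone arm's microbial share.

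**The case against.** The strongest reply is that the documents do not show that the bias occurs, let alone which arm it favours. They give no human-read share and no effect of ceftriaxone on it. Section 2.5 notes that controls may receive longer broad-spectrum courses because of more pneumonia, so the contrast in bacterial load could shrink or reverse, especially at the last swab. This stands: a reader might infer that the bias is differential and favours ceftriaxone, but that is only a possibility.

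The count is also not the only measure, since Section 9.5 plans an abundance comparison. That is correct, but without a denominator the abundance comparison does not supply the missing standardisation.

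Model 1 does not represent the feared scenario either. If resistant bacteria survive preferentially, their share rises and offsets lost depth. In the enrichment run a twofold loss still showed an increase and a threefold loss left the count nearly flat. So masking is possible, but a threefold loss of reads halving the ARG count is not a general result.

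Part of any fall may be a true loss of ARG-carrying bacteria. The plan cannot separate the two.

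Finally, the resistome is not among the primary, secondary or safety outcomes in Section 3.11, although it is in the trial title and the hypothesis. That limits the weight of the point but does not remove it.

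**Conclusion.** The point holds as a gap in the analysis. Followed as written, the count comparisons in Section 9.5 mix resistance with microbial depth, and nothing in the plan separates them. If ceftriaxone lowers microbial reads, the count is biased toward the hypothesis in Section 2.7.

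The size runs from a few per cent, where ARGs sit on abundant genomes and the shift in human share is moderate, to a loss of half or more in diverse communities with a large drop in microbial reads. It is small where human DNA is negligible. Every figure rests on assumed community structure, genome size, coverage threshold and microbial share.

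It would also go too far to read the 20 million reads in Section 2.5 as a total before human removal, because the text does not define them. The primary outcome and its sample size are unaffected.

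**What to change.** In Sections 4.2 and 9.5:

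1. Report non-human reads per sample by arm and visit, and state what the 20 million reads refer to.
2. Express genotype abundance per million non-human reads or per genome equivalent.
3. Repeat the ARG count and change-from-baseline analyses on reads subsampled to a common non-human depth, and compare the change between arms. Choose that depth from read counts pooled over both arms, before ARG results are seen by arm.
4. A depth floor may exclude more samples from one arm and break baseline pairs. Report exclusions by arm, and add an analysis that keeps all samples with non-human read count as a covariate. Treat that analysis as supportive, since read count is itself measured after randomisation.
5. Show the unstandardised count alongside, and do not conclude that there is no negative effect from it alone.

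The cost is extra bioinformatics on existing FASTQ files, with no new samples or sequencing. Some rare ARGs are lost at the common depth, and per-read measures do not capture a true fall in absolute ARG burden.
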